### **13.3 Planned efficacy/outcome analyses**

The efficacy variables will be analyzed as described below using the FAS.

Total seizure frequency per 28 days will be derived from the seizure count information recorded on the diary card and is defined as the number of seizures standardized to a 28-day period. It is computed as the number of seizures recorded over a period, divided by the total number of days in that period, multiplied by 28. Observable focal-onset seizures refers to Type IA1, IB, and IC seizures (according to the ILAE Classification of Epileptic Seizures, 1981). Focal-onset seizures include all Type I seizures. Seizure-free status and seizure-free days include all (Type I, II, and III) seizure types.

#### **13.3.1 Analysis of the primary efficacy variable**

All analyses of the primary efficacy variable will be repeated on the PPS.

In the event that enrollment is completed in China and Europe/North America/Japan at approximately the same time, a single analysis will be conducted including all randomized subjects. If the enrollment period in China is extended to attain the target of approximately 100 subjects randomized in that country, then 2 analyses will be carried out in a sequential fashion with statistical significance required from the first analysis in order for the second analysis to take place. For analyses to support European/North American/Japanese regulatory submissions, the primary analysis will be carried out with a significance level of 0.05 when all randomized (approximately 400) non-Chinese subjects have completed or terminated the study. If the first analysis reaches statistical significance, a subsequent analysis will be carried out for all randomized (approximately 500) subjects (at the 0.05 significance level) to support the submission for China. If the first analysis does not reach statistical significance, no further testing will be done, for either the European/North American/Japanese regulatory submissions or for the Chinese submission.

##### **13.3.1.1 Analysis of the primary efficacy variable for the US FDA, PMDA, Chinese FDA, and other regulatory authorities not specified in Section 4.1.1.2**

Pairwise comparisons of 400mg bid, 200mg bid, and 100mg bid dose groups versus placebo will be carried out using the following analysis model. Type 1 error will be controlled by the Hochberg step-up procedure within SAS® Proc Multtest.

For the US FDA, PMDA, Chinese FDA, and other regulatory authorities not specified in Section 4.1.1.2, the primary efficacy variable is the change in log-transformed observable focal-onset seizure frequency from Baseline, over the 12-week Maintenance Period. The 28-day Baseline and post-Baseline (maintenance) seizure frequency will be transformed with the natural logarithm, specifically  $\ln(x+1)$ , where x represents the 28-day seizure frequency. The transformed seizure frequency data will be analyzed using analysis of covariance (ANCOVA)

with treatment group as the main factor, Baseline log-adjusted seizure frequency as a continuous covariate, and Baseline SV2A and region used as a categorical factors. Pairwise contrasts will be constructed to compute estimated effects of each dose from placebo.

All pairwise analyses of the primary efficacy variable will be repeated on the PPS.

If the second analysis is performed for Chinese FDA (Section 13.3.1), a dose will be concluded statistically significant in the second analysis only if the dose is statistically significant in the first and second analyses.

### **13.3.1.2 Analysis of the primary efficacy variable for EMA and regulatory authorities who reference EMA**

For EMA and regulatory authorities who reference EMA, the primary efficacy variable will be the 75% responder rate in observable focal-onset seizures during the Maintenance Period and will be analyzed using logistic regression with factors for treatment group, Baseline seizure frequency, and Baseline SV2A use. If there are issues with convergence, Baseline SV2A use and region will be dropped.

The same methodology carried out in Section 13.3.1.1 for US FDA, PMDA, Chinese FDA, and other regulatory authorities will be applied to the pairwise analyses.

### **13.3.2 Secondary efficacy analysis**

#### **13.3.2.1 Secondary efficacy variables for the US FDA, PMDA, Chinese FDA, and other regulatory authorities not specified in Section 4.1.1.2**

The 75% responder rate in observable focal-onset seizures during the Maintenance Period is a secondary efficacy variable for the FDA. It is the primary efficacy variable for EMA. The analyses are described in Section 13.3.1.2.

In addition, the 50% responder rate in observable focal-onset seizures during the Maintenance Period will be analyzed using logistic regression as described in Section 13.3.1.2.

Analyses of the percent change in seizure reduction endpoints will be performed using the Wilcoxon-Mann-Whitney test. The Hodges-Lehmann nonparametric estimator will be used to estimate the median percent reduction in seizures between groups and its corresponding 95% CI will be provided.

#### **13.3.2.2 Secondary efficacy variables for EMA and regulatory authorities who reference EMA**

The change in log-transformed observable focal-onset seizure frequency from Baseline over the 12-week Maintenance Period is a secondary efficacy variable for EMA. It is the primary efficacy variable for the FDA. The analyses are described in Section 13.3.1.1.

In addition, the 50% responder rate in observable focal-onset seizures during the Maintenance Period will be analyzed using logistic regression as described in Section 13.3.1.2.

Analyses of the percent change in seizure reduction endpoints will be performed using the Wilcoxon-Mann-Whitney test. The Hodges-Lehmann nonparametric estimator will be used to estimate the median percent reduction in seizures between groups and its corresponding 95% CI will be provided.

### **13.3.3 Other efficacy analyses (this applies for all regulatory authorities)**

All other analyses of the 75% and 50% responder rate endpoints will be analyzed using the same logistic regression model as specified in Section 13.3.1.2. Analyses of 90% responder rate and seizure freedom will use the same methodology. In addition to observable focal-onset seizures and focal-onset seizures, analyses will also be carried out on all seizures (seizure-free status and seizure-free days) during the 12-week Maintenance Period and the 16-week Treatment Period.

All other analyses of the change from Baseline in seizure frequency will be analyzed using the ANCOVA model on the log-transformed data, as specified in Section 13.3.1.1.

The time-to-return to Baseline observable focal-onset seizure frequency will be analyzed using Kaplan-Meier methodology. Additional details of the analysis will be captured in the SAP.

The QOLIE-31-P and SSG assessments will be summarized using descriptive statistics by each available visit.

## **13.4 Planned safety and other analyses**

### **13.4.1 Safety analyses**

Adverse events will be coded using the Medical Dictionary for Regulatory Activities (MedDRA®). Adverse events will be summarized by MedDRA System Organ Class and Preferred Term. The incidence of SAEs, AEs leading to premature discontinuation or dose tapering, and related AEs, and the incidence of AEs by maximum intensity, will also be summarized.

Laboratory values, ECG data (heart rate, PR interval, QRS duration, QT interval, QTcB or QTcF, and Investigator's conclusion on ECG profile) and arrhythmias, vital signs, weight, and changes from Baseline in these measures will be summarized by period, visit, and treatment group. Possibly clinically significant treatment-emergent abnormalities for laboratory values, vital signs, and weight will be listed and summarized by period and visit for each treatment group.

Electrocardiogram abnormalities as well as physical and neurological abnormalities will also be listed by period and visit. Quantitative safety parameters will be summarized descriptively by time point and treatment group. Categorical safety summaries will provide the number and percentage of subjects within each summarized category.

Doppler echocardiogram results at Baseline and during and after treatment, and changes from Baseline, will be listed and descriptively summarized.

All C-SSRS data obtained at Baseline and subsequent visits will be reported as a listing ordered by subject and visit. Psychiatric and Mental Status assessment and CIWA-B data will also be included using listings.

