clinically significant echocardiogram findings (only minor/trace or Grade 1 findings) have been observed. Based on vital signs, ECGs, echocardiograms, and cardiovascular TEAEs evaluated in clinical studies to date, there is no evidence that PSL causes cardiovascular harm in study participants. Data from in vitro studies and clinical pharmacology studies in healthy study participants and epilepsy patients have shown that PSL at high doses moderately increased exposure of sensitive substrates of cytochrome P450 (CYP)2C19. Although less clear, strong inhibitors and inducers of CYP2C19 may also impact the PK and metabolism of PSL and metabolites. Strong inducers of CYP3A4 have also been shown to have a significant interaction with PSL. Therefore, concomitant administration of strong inducers and inhibitors of CYP3A4 with PSL is prohibited. Additionally, when moderate CYP3A4 inhibitors are introduced or withdrawn from a study participant's treatment regimen, the study participant should be closely monitored for changes in clinical response and tolerability. Risks associated with suicidal ideation and behavior, pregnancy and lactation, worsening of seizures, and potential overdose are common to all AEDs.

Risk minimization activities for all relevant risks include study protocol inclusion, exclusion, and withdrawal criteria, and safety monitoring measures as deemed appropriate. The routine core pharmacovigilance activities include: signal detection for any new and existing safety concerns, specific follow-up, and aggregate reporting as well as questionnaires for suicidality, withdrawal symptoms, psychiatric and mental status, and anxiety and depression.

Additional routine risk minimization activities include: ICFs that describe the applicable potential risks and discomforts and risks associated with procedures; inclusion, exclusion, and withdrawal criteria and safety monitoring measures as deemed appropriate in clinical study protocols; ECG monitoring for arrhythmias; and clinical laboratory panels for hepatotoxicity. Study participants will also have routine echocardiograms performed, which provide a grading for valvular findings and/or the presence of any accompanying clinical signs/symptoms.

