### **6.3 Withdrawal criteria**

Subjects are free to withdraw from the study at any time, without prejudice to their continued care.

Subjects should be withdrawn from the study if any of the following events occur:

1. Subject withdraws his/her consent.
2. The Sponsor or a regulatory agency requests withdrawal of the subject.
3. Subject is noncompliant with the study procedures or medications in the opinion of the Investigator.
4. Subject takes prohibited concomitant medications, prescribed or over-the-counter, as defined in this protocol.
5. Subject develops an illness that would interfere with his/her continued participation.

6. A prolongation or worsening of overall seizure duration, frequency, type, or pattern considered by the Investigator as serious enough to warrant discontinuation from the study.
7. Subject with an echocardiogram showing a Grade 2 finding (moderate regurgitation/stenosis) if accompanied with moderate to severe signs/symptoms or a Grade 3 finding (severe regurgitation/stenosis) will be discontinued from the study regardless of accompanying clinical symptoms, and should begin discontinuation of the IMP. Additionally, a jump of 2 grades, from Grade 0 to Grade 2 (moderate regurgitation/stenosis) accompanied with moderate to severe symptoms or from Grade 1 to Grade 3 (severe regurgitation/stenosis) will result in subject discontinuation (see Section 6.3.2).
8. Changes in the ECG that are regarded as clinically significant and/or that worsen over time.
  - An ECG shows an absolute value for QTcB or QTcF  $\geq 500$ ms or  $\geq 60$ ms above Baseline.
  - Subject develops second- or third-degree atrioventricular block or another clinically relevant change in ECG as determined by the Investigator.
9. Subject has active suicidal ideation without a specific plan as indicated by a positive response (“Yes”) to question 4 of the “Since Last Visit” version of the C-SSRS. The subject should be referred immediately to a mental healthcare professional and may be withdrawn from the study based upon the Investigator’s judgment of benefit/risk of continuing the subject in the study/on IMP.

Subject has active suicidal ideation with a specific plan as indicated by a positive response (“Yes”) to question 5 of the “Since Last Visit” version of the C-SSRS. The subject should be referred immediately to a mental healthcare professional and must be withdrawn from the study.

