### **11.7.2 Electrocardiograms**

The 12-lead ECG recordings will be measured by a qualified technician at the scheduled time points presented in [Table 5-1](#).

All ECG recordings will be performed with the subject resting in the supine position for at least 5 minutes. Each ECG will be recorded at a speed of 25mm/s and with a calibration of 1cm/mV.

The Investigator should review all ECG recordings and determine if there are any abnormalities that are considered clinically significant for a particular subject. Electrocardiograms will also be sent to a specified central reader for review as detailed in the ECG Manual. The following ECG parameters will be recorded: heart rate, PR interval, QRS duration, QT interval, QTcB or QTcF, and Investigator's conclusion on ECG profile.

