10.4.2 Electrocardiograms

ECG parameters include heart rate, PR interval, QRS duration, QT interval, QTcB [QT corrected for heart rate using Bazett's formula], and QTcF [QT corrected for heart rate using Fridericia's formula].

The observed ECG parameter values and their change from Baseline will be summarized (SS) descriptively by treatment group and PSL total group for each scheduled assessment visit. The Last Visit, minimum, and maximum post-baseline values during the Treatment Period will also be included. In addition, the number and percentage of subjects with QTc (Bazett and Fridericia corrected) classifications of <450ms, 450 to <480ms, 480 to <500ms, and ≥ 500 ms and change from baseline of <30ms, 30 to <60ms, and ≥ 60 ms will be presented for each visit.

For each ECG, the overall ECG result, is also collected, categorized as one of: no abnormality, an abnormal but not clinically significant finding, or a clinically significant finding. The number and percentage of subjects with no abnormality, an abnormal but not clinically significant finding, and a clinically significant finding will be summarized for each of the scheduled assessment visits. Percentages for the visit will be relative to the number of subjects with an ECG result for the visit.

The number and percentages of subjects with abnormal ECG during the Treatment Period will be presented by treatment group and PSL total group. The abnormal ECG criteria are provided in Appendix 13.3. Subject numbers for those meeting abnormal criteria will also be presented.

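### The protocol promises an arrhythmia summary by treatment group, but no listed ECG item feeds it, no SAP table delivers it, and the SAP does not declare that it was dropped

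*Protocol*

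**What the plan says.** Protocol 13.4.1 deals with adverse events in one paragraph. In the next it turns to laboratory values and to ECG data, for which it lists heart rate, intervals and the Investigator's conclusion. It then adds a further item: "arrhythmias, vital signs, weight, and changes from Baseline in these measures will be summarized by period, visit, and treatment group". Arrhythmias are thus named separately from adverse events and from the Investigator's conclusion.

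Protocol 2.4 includes "ECG monitoring for arrhythmias" among the risk-minimisation activities. In Protocol 6.3, criterion 8 covers the case in which "Subject develops second- or third-degree atrioventricular block or another clinically relevant change in ECG" is found.

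On data collection, Protocol 11.7.2 states: "The following ECG parameters will be recorded: heart rate, PR interval, QRS duration, QT interval, QTcB or QTcF", followed by the Investigator's conclusion. It adds: "Electrocardiograms will also be sent to a specified central reader for review as detailed in the ECG Manual".

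On analysis, SAP 10.4.2 opens with "ECG parameters include heart rate, PR interval, QRS duration, QT interval, QTcB" and then QTcF. It plans four outputs:
- descriptive statistics for these parameters;
- QTc classes;
- a three-level overall result at each scheduled visit;
- a count of subjects with an abnormal ECG by treatment group and padsevonil total.

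The limits for that last count are in SAP 14.4. They cover QT, QTcF, QTcB, PR, QRS and heart rate.

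**The concern.** A summary promised in the protocol has no listed data item behind it and no table in front of it. Several rhythm findings need not cross any limit in SAP 14.4: rate-controlled atrial fibrillation, ectopy, or second-degree AV block at a rate of 50 or more. They would appear in the overall result only as abnormal, without type.

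The protocol itself treats rhythm as important. Section 2.3.1 reports a cardiology opinion that found no clear evidence of increased ectopy or clinically significant arrhythmia, and says that cardiac monitoring will continue in order to understand the risk better. A randomised comparison with placebo could inform that opinion. The stake is a safety count that the tracings could support and that the report, if it follows the SAP as written, would not contain.

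**Working it through.** The plan gives no figure to reproduce, so the main check compares what is promised with what is delivered.

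1. **Promise.** Protocol 13.4.1: arrhythmias, with change from Baseline, by period, visit and treatment group.
2. **Data item.** Protocol 11.7.2: rate, PR, QRS, QT, QTc and the Investigator's conclusion. No rhythm or conduction finding is listed. A central read exists, but its content is in an ECG Manual that is not among the documents.
3. **Tables.** SAP 10.4.2: parameters, QTc classes, three-level result and threshold counts. SAP 14.4: limits on rate (<50, >120) and intervals only. There is no arrhythmia table.
4. **Declaration.** SAP 3.9 tabulates changes from the protocol analyses. It has no row for ECG or arrhythmias.

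Next, the routes by which an arrhythmia could still reach a comparison by arm:

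- **Adverse events.** SAP 10 and 10.2 tabulate treatment-emergent events by system organ class and preferred term for each group. An arrhythmia reported as an adverse event is counted with its type. But Protocol 11.7.1, 11.7.4 and 11.7.5 each instruct that clinically significant vital sign abnormalities, or examination changes, be recorded as adverse events. Protocol 11.7.2 has no such sentence for ECGs, so this route may miss some findings.
- **Overall ECG result.** This is counted at each scheduled visit, without type and without shift from Baseline. Exclusion criterion 13 still admits sinus arrhythmia, rare ectopy and bundle branch blocks not judged clinically significant (with PR below 220 ms). In the middle category, old and new findings are therefore mixed.
- **Threshold counts.** These catch an arrhythmia only if it moves rate, PR, QRS or QT past a limit.
- **Listings.** Protocol 13.4.1 also lists ECG abnormalities by period and visit. A listing gives no incidence by arm.

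Scale, from planned enrolment (Protocol 13.8: 100 per arm, so 300 padsevonil and 100 placebo outside China). Table 5-1 and Section 8.2 schedule on-treatment ECGs at Visits 3, 4, 5 and 7, which is 4 per completer:

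- padsevonil: 4 × 300 = 1,200 tracings
- placebo: 4 × 100 = 400 tracings

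If no treatment-emergent arrhythmia were seen in n padsevonil subjects, the one-sided 95% upper bound is 1 − 0.05^(1/n):

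- n = 300 (planned): 1 − 0.05^(1/300) = 0.99%
- n = 200 (assumed): 1 − 0.05^(1/200) = 1.49%
- n = 100 (assumed): 1 − 0.05^(1/100) = 2.95%

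The two smaller values only show how the bound widens. The documents do not give the number actually exposed.

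**The case against.** The strongest reply is that a comparison with placebo survives. All treatment-emergent events are tabulated by preferred term and arm. Protocol 11.1.1.1 defines an adverse event broadly enough to include a new atrial fibrillation or AV block. The Investigator reviews every tracing, and the DMC monitors cardiac events in particular (Protocol 13.7). Exclusion criterion 13 removes most clinically significant rhythm and conduction disease at entry, so a clinically significant result after Baseline is mostly new, and randomisation balances the remainder. All of this stands. A reader might infer from the missing table that new arrhythmias on padsevonil cannot be compared with placebo at all. The documents do not support that.

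A reader might also infer that rhythm was never recorded. That does not follow either. The ECG Manual and the eCRF are not available, and either may hold a rhythm finding.

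Two further replies carry less weight. SAP 1 says that the protocol analyses apply unless otherwise specified, and SAP 3.1 says that CRF data will in general be listed. The first leaves the commitment formally in place but specifies no table, and the second yields no count by arm. It is also fair to say that ECG monitoring as a risk control in Protocol 2.4 works at subject level and promises no analysis by arm. That promise comes from 13.4.1 alone, which is enough.

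**Conclusion.** The point holds as an undeclared gap between protocol and SAP. Arrhythmias found on ECG would be compared with placebo only if reported as adverse events, or inside an abnormal or clinically significant ECG category that does not say what the abnormality was. The systematic treatment-emergent count by arm is lost.

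The gap is modest and does not touch the efficacy analyses. It is still worth repairing, because the lost item is a promised safety summary and one table would restore it.

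The 1,200 and 400 tracings and the 0.99% bound rest on planned enrolment, full completion and, for the bound, zero events. SAP 3.9 records early termination, so the tracings may be fewer and the bound wider. The bound would describe detection on brief scheduled tracings, not the true incidence of arrhythmia. Whether a rhythm field already exists is unknown, and that decides which of the two remedies applies.

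**What to change.** If rhythm or abnormality findings are held from the Investigator or the central read:
- In SAP 10.4.2, add the number and percentage of subjects with a treatment-emergent arrhythmia or conduction abnormality. Define this as absent on all pre-dose ECGs and present on any post-Baseline ECG in the Treatment Period, scheduled or unscheduled. Present it by arm and padsevonil total.
- Add the by-visit summary that Protocol 13.4.1 promises.
- Name the data item in Protocol 11.7.2.

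If no such item was captured for visits already done, add a row to SAP 3.9 stating that the 13.4.1 arrhythmia summary is replaced by treatment-emergent adverse events and the overall ECG result. Changing 11.7.2 cannot create data for past visits.

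In the same edit, correct the pointer in SAP 10.4.2 to Appendix 13.3. The ECG limits are in 14.4.

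The cost is the extra tabulation and possibly the coding of free-text ECG findings. No additional ECG is needed.
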